### 1.2.2 Randomisation

Participants will be randomised 1:1; stratified by gender (male; female) and ethnicity (White European; other) to either intervention or control groups.

If two people are taking part from the same household they will be randomised to the same arm to prevent contamination taking place.

Both control and intervention participants will be informed of the outcome of the randomisation. In addition intervention participants will be sent a letter confirming the date and the venue of the education sessions.

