### **1.2.6** Sample size calculations

The primary outcome is change from baseline to 12 months average daily physical activity, as quantified by the Euclidean norm minus one (ENMO) method measured in milligravity units (mg). This is the main measure of activity derived from the activity monitor. In order to detect a minimum clinically significant difference of 2.1 mg, which is equivalent to an overall increase in physical activity volume of approximately 30 minutes of light walking at 4km/h, assuming a standard deviation of 5.3 mg [1], a power of 80% and significance level of 5%, the sample size requires 202 participants. To allow for 20% loss to follow-up and 20% non-compliance of the activity monitor, we will therefore need to recruit 338 participants (169 in each group).

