# 3.3 Intention-to-treat Population/Full analysis set

The intention-to-treat (ITT) analysis population will consist of all participants randomised. Participants will be analysed in the group to which they were randomly allocated and regardless of any protocol deviations or violations. Multiple imputation methods will be used to impute missing outcome data. This will be a sensitivity analysis.

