# **4** General Issues for Statistical Analysis

### 4.1 Multiplicity, Multiple Comparisons and Interim Analyses

All tests and reported p-values will be two-sided, where a p-value of < 0.05 will be considered to be statistically significant. Estimates will be presented with 95% confidence intervals. There will be no formal adjustment for multiple significance testing. The outcomes however, are clearly categorised by the degree of importance (primary and secondary). No formal interim analyses were planned.

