#### 4.5.2.2 Intention-to-treat Population

To allow for full analysis set, missing data will be imputed using a multiple imputation procedure which substitutes predicted values from a regression equation. The imputation will be carried out by the MI command in Stata . MI replaces missing values with multiple sets of simulated values to complete the data, performs standard analysis on each completed dataset, and adjusts the obtained parameter estimates for missing-data uncertainty using Rubin's rules to combine estimates .

The following procedure will be followed:

- The MI will be set as wide
- The MI will register imputation of the overall volume of physical activity at 12 months and at baseline
- A regression method will be used , where the registered variables will be individually adjusted for the randomisation and stratification factors (sex and ethnicity), with 100 imputations to avoid biased estimates, rseed (2259) and the force options
- MI estimate will provide the final results using the same regression model as the primary analysis and covariate adjustments.

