#### 4.5.2.3 Exploratory analysis of number of sessions attended

We will assess the effect of the number of sessions attended on the primary and secondary outcomes of the physical activity using the same model used in the primary analysis. We will assess three alternative scenarios

- I. <1, no sessions attended
- II. 1-3 sessions attended
- III. All 4 sessions attended

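### The ITT multiple imputation leaves out session attendance, so if non-attenders are missing more often and benefit less, it repeats the complete-case bias instead of testing it

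*SAP*

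**What the plan says.** Section 3.3 defines the ITT set as everyone randomised: "Participants will be analysed in the group to which they were randomly allocated and regardless of any protocol deviations or violations". Section 2.1 gives the purpose of imputing: to see whether the complete-case primary result is robust to missing data.

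Section 4.5.2.2 registers two variables for imputation, activity volume at 12 months and at baseline. Of the predictors it says the "registered variables will be individually adjusted for the randomisation and stratification factors (sex and ethnicity". Attendance is not among them. The completed data are then analysed with the primary model of section 4.5.1, which also adjusts for baseline activity and for change in accelerometer wear time.

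The plan relies on attendance elsewhere. Section 3.4 defines the per-protocol intervention group by at least one session, and section 4.5.2.3 states: "We will assess the effect of the number of sessions attended on the primary and secondary outcomes of the physical activity", in categories of 0, 1-3 and 4 sessions.

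Section 1.2.6 sets the expected scale of missing outcomes: "To allow for 20% loss to follow-up and 20% non-compliance of the activity monitor".

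**The concern.** An intervention participant who attended nothing and has no 12-month monitor data is imputed from observed intervention participants of the same sex and ethnicity. If people who disengage from the programme are also less likely to return or to wear the monitor, those observed participants over-represent attenders. The imputed values then credit non-attenders with benefit from sessions they did not receive.

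The complete-case analysis has the same over-representation. Section 4.5.2.2 is the only analysis in the SAP that does anything about missing outcomes: the per-protocol analysis again uses complete data, and no delta-adjusted or reference-based analysis is planned. Agreement between the complete-case and imputed results would therefore look reassuring while saying little about this particular threat, even though the variable that could expose it is available.

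**Working it through.** **Inputs from the SAP.** Section 1.2.6: "minimum clinically significant difference of 2.1 mg"; "assuming a standard deviation of 5.3 mg [1], a power of 80% and significance level of 5%, the sample size requires 202 participants". Section 4.1: "All tests and reported p-values will be two-sided". Section 1.2.2: "Participants will be randomised 1:1". Section 1.2.6 also gives 338 to be recruited, 169 per group.

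**The plan's own figures.** The normal formula gives 2 × (1.960 + 0.842)² × (5.3/2.1)² ≈ 100 per arm (200). The t-based version gives 100.96, so 101 per arm, or 202, which matches. Inflation: 202/(1 − 0.40) = 336.7, so 169 per arm, or 338, which matches. Multiplying the two rates instead gives 202/(0.8 × 0.8) = 316, which does not. The SAP therefore plans for 40% missing primary outcomes.

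**Formula.** In the intervention arm let a be the proportion attending at least one session and q = 1 − a. Let mA and mN be the proportions missing the outcome among attenders and non-attenders, and dA and dN their effects.

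- True ITT effect = a·dA + q·dN
- Attender share among those observed: s = a(1 − mA) / [a(1 − mA) + q(1 − mN)]
- Complete-case effect = s·dA + (1 − s)·dN
- Imputing on arm alone sets the mean of the imputed values to the observed arm mean, so its expected effect is the same. Sex and ethnicity alter this only if they predict attendance.
- Bias = (s − a)(dA − dN)

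The bias is positive only if non-attenders are missing more often (s > a) and benefit less (dA > dN).

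**Numbers.** The SAP gives no attendance rate, no missingness by attendance and no effect by attendance, so these are assumptions: dA = 2.1 mg, dN = 0.

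| q | mA / mN | s | True (mg) | Complete case and planned MI (mg) | Bias (mg) |
|---|---|---|---|---|---|
| 10% | 35% / 60% | 0.94 | 1.89 | 1.97 | +0.08 (+4%) |
| 20% | 35% / 60% | 0.87 | 1.68 | 1.82 | +0.14 (+8%) |
| 30% | 35% / 60% | 0.79 | 1.47 | 1.66 | +0.19 (+13%) |
| 10% | 30% / 80% | 0.97 | 1.89 | 2.04 | +0.15 (+8%) |
| 20% | 30% / 80% | 0.93 | 1.68 | 1.96 | +0.28 (+17%) |
| 30% | 30% / 80% | 0.89 | 1.47 | 1.87 | +0.40 (+27%) |
| 10-30% | 40% / 40% | 0.90-0.70 | 1.89-1.47 | as true | 0 |
| 10% | 60% / 30% | 0.84 | 1.89 | 1.76 | −0.13 (−7%) |
| 20% | 60% / 30% | 0.70 | 1.68 | 1.46 | −0.22 (−13%) |
| 30% | 60% / 30% | 0.57 | 1.47 | 1.20 | −0.27 (−18%) |

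Second row worked: s = 0.8 × 0.65 / (0.8 × 0.65 + 0.2 × 0.40) = 0.52/0.60 = 0.867; 0.867 × 2.1 = 1.82; true 0.8 × 2.1 = 1.68. Overall missingness in the intervention arm is 35% to 45% in the six inflated rows and 51% to 57% in the three reversed rows.

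**Simulation.** 338 participants, 400 trials, 20 imputations, 40% missing in controls, and an analysis model with baseline activity but no wear-time term. Mean estimates in mg:

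| q, mA / mN | Full data | Complete case | Planned MI | MI adding attendance and baseline activity |
|---|---|---|---|---|
| 20%, 40% / 40% | 1.68 | 1.67 | 1.69 | 1.66 |
| 20%, 35% / 60% | 1.73 | 1.88 | 1.90 | 1.74 |
| 30%, 30% / 63% | 1.44 | 1.68 | 1.67 | 1.44 |

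The empirical SD of planned MI was 0.90 to 0.93, so the Monte Carlo error of each mean is about 0.93/√400 ≈ 0.05. Planned MI follows the complete-case estimate, and adding attendance recovers the full-data value. Baseline activity was generated independently of attendance and missingness, so it cannot account for that recovery. The reversed pattern rests on the closed form alone.

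**Limit of the remedy.** With q = 20% and 60% of non-attenders missing, 169 × 0.20 × 0.40 ≈ 13.5 non-attenders are observed. With 80% missing, 169 × 0.20 × 0.20 ≈ 6.8. In that last scenario the simulated attendance model became singular, which happens when no non-attender is observed.

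**The case against.** A reader might infer that the imputation necessarily inflates the effect. The SAP does not support that. Inflation needs both more missingness and less benefit among non-attenders; both are plausible, neither is stated, and the direction can reverse.

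A reader might also infer a breach of the ITT definition. There is none: imputing within the randomised arm is consistent with section 3.3. Nor does the imputation create the bias. The complete-case primary analysis already carries it, and this is a sensitivity analysis.

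Extending the argument to people who stopped part-way is not supported either. The calculation has two groups only, and section 1.2.3 provides text messages after the first session, so zero benefit cannot be assumed for partial attenders.

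The bias is also modest against sampling error: 1.88 − 1.73 = 0.15 mg and 1.68 − 1.44 = 0.24 mg, against an empirical SD of the complete-case estimate of about 0.8 mg.

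The strongest objection concerns wear time. The final model includes change in wear time, which is not registered for imputation and is unavailable for anyone without 12-month monitor data. Read literally, those participants leave the final regression, their imputed values contribute nothing, and adding attendance alone would change little.

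All of this stands and limits the claim. It does not remove the point that a recorded, plausible predictor of both outcome and missingness is left out of the plan's only missing-data check.

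**Conclusion.** The point holds in conditional form. As written, the ITT imputation cannot detect bias from attendance-related missingness, because it returns nearly the complete-case estimate. If non-attenders are missing more often (35% v 60% up to 30% v 80%) and only attenders gain 2.1 mg, the estimate exceeds the true ITT effect by 0.08 to 0.40 mg (+4% to +27%) at 10% to 30% non-attendance. Equal missingness gives no bias. The reversed pattern (60% v 30%) gives −0.13 to −0.27 mg. All these rates are assumptions. At the planned 40% missing outcomes, an inexpensive improvement to the sensitivity analysis is worthwhile; the evidence does not show that the trial's result will be overstated.

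**What to change.** Amend section 4.5.2.2 as follows.

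1. Impute 12-month activity separately by arm. In the intervention arm add attendance as a predictor: 0 versus at least 1 session, or 0, 1-3 and 4 where numbers allow. Keep attendance out of the analysis model, so that the estimate remains the randomised comparison.
2. State how change in wear time is handled in the imputed analysis, for example by imputing it or by leaving it out of that model. Without this, step 1 has little effect.
3. Tabulate missing 12-month outcomes by attendance category.
4. State in advance what happens if too few non-attenders are observed to support the imputation: use control-based or delta-adjusted imputation for them. Collapsing categories does not help here, because the zero-session group is the sparse one. A control-based rule assumes that non-attenders change as controls do, and the report should say so.

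The cost is SAP wording and a few lines of code, with no new data. A separate simulation without covariates put the rise in the MI standard error from adding attendance at about 1% to 3% (for example 0.758 to 0.774); a model with three attendance categories could cost more. The downside is a slightly wider interval and a possibly smaller ITT estimate. If missingness turns out to be unrelated to attendance, almost nothing is lost.

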#### 4.5.2.3 Exploratory analysis of number of sessions attended

We will assess the effect of the number of sessions attended on the primary and secondary outcomes of the physical activity using the same model used in the primary analysis. We will assess three alternative scenarios

- I. <1, no sessions attended
- II. 1-3 sessions attended
- III. All 4 sessions attended

#### 4.5.2.4 Stratified analyses

Interaction effects will be fitted between intervention arm and gender (male vs. female) and ethnicity (White European vs. other). If the interaction term is statistically significant at the 10% level then stratified analyses will be performed for that factor using the same model as the primary analyses.

### 4.6 Secondary Endpoint Analyses

The analyses of the secondary outcomes will be conducted in a similar manner as the main analysis using the appropriate model type, logistic regression for binary outcomes, linear for continuous and ordinal for ordinal outcome.

The assumptions of each analysis will be assessed and alternate parameterisations will be considered where appropriate.

# 4.7 Subgroup Analyses

We will conduct the following subgroup analyses to assess if the intervention effect is statistically different between these groups.

- Age
- Sex
- Median number of comorbidities
- Depression
- Arthritic condition
- Cardiovascular condition
- Type 2 diabetes
- Physical activity; low and high

The main analysis for each subgroup will involve using the same analytic principles as the primary analysis, but stratifying by the subgroup to estimate the mean difference in the overall volume of physical activity when compared to the control group. Further subgroup analyses will investigate the interaction effects between the treatment and subgroup, this will include an additional interaction term to the model; 'subgroup × treatment'. Subgroup results will be graphically presented as forest plots, with the estimated difference of overall volume of physical activity between treatment groups with 95% confidence interval for the interaction.

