### 1.2.4 Inclusion Criteria

Patients will be included in the study based on the following criteria:

- Good understanding in written and verbal English;
- Able to give informed consent;
- 40-85 years old inclusive;
- Have two or more chronic conditions (see *table1* in MAP protocol v6;20.6.2018)
- Have access to a mobile phone for use in potential study activities;
- Able to walk independently;

There are no limitations with disease duration, medication use and/or initiation of new treatment unless there are specific recommendation for bed rest and minimising physical activity for a specific condition.

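### Section 4.7 tests effect modification by number of conditions, physical activity and apparently age in groups; continuous interaction terms would be more efficient if modification is roughly linear, and would not need the unstated cuts

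*SAP*

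**What the plan says.** Section 4.7 gives the purpose: "We will conduct the following subgroup analyses to assess if the intervention effect is statistically different between these groups". It lists eight factors, three of which are by nature continuous or counts:

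- Age, with no categories and no cut.
- "Median number of comorbidities", which reads as a split at the median.
- "Physical activity; low and high", with no threshold, measure or time point.

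The main subgroup analysis works by "stratifying by the subgroup to estimate the mean difference in the overall volume of physical activity when compared to the control group". A further analysis tests for interaction: "this will include an additional interaction term to the model; 'subgroup × treatment". Results are shown as forest plots. No interaction with a modifier in continuous form is planned.

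On the error rate, section 4.1 says "All tests and reported p-values will be two-sided, where a p-value of < 0.05 will be considered to be statistically significant" and "There will be no formal adjustment for multiple significance testing".

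**The concern.** Interaction tests have low power in a trial sized for a main effect, and grouping a continuous modifier usually lowers it further. The data for the finer test are already collected. Age runs over a wide range ("40-85 years old inclusive", section 1.2.4), the number of conditions is a count, and baseline activity volume is already an adjustment term in the primary model (section 4.5.1).

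The second issue is pre-specification. Where a cut is not fixed beforehand, it can be chosen after the data are seen, and that choice can create or hide a difference. Activity is the most open factor, because section 2.2 collects accelerometer volume, intensity categories and the RPAQ. At stake is the credibility of the effect-modification results.

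**Working it through.** **Inputs.** From SAP 1.2.6: target difference 2.1 mg, SD 5.3 mg, 80% power, 5% significance, 202 evaluable, 338 recruited. From 1.2.2: 1:1 allocation. From 4.1: two-sided 0.05. The modifier distributions below are assumptions; the SAP gives none.

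**Reproducing the plan's figure.** A two-sample t-test calculation with 2.1 and 5.3 mg gives 100.96, so 101 per arm and 202 in total, as stated. Then 202 / (1 − 0.40) = 336.7, or 169 per arm and 338 in total, also as stated. The SAP gives no power figure for the subgroup tests.

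**Information kept by a split.** If the effect changes linearly with the modifier, the share kept is the squared correlation between the modifier and its group indicator. For a normal modifier cut at quantile q this is φ(z_q)² / [q(1 − q)]. At the median it is 2/π = 0.637, a loss of 36.3%. Other assumed cases:

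| Modifier (assumed) | Cut | Loss |
|---|---|---|
| Uniform | median | 25% |
| Lognormal, log-SD 0.4 | median | 44% |
| Age, normal (65, SD 9) truncated to 40–85 | median | 34% |
| Same | 60 | 41% |
| Same | 70 | 43% |
| Same | 75 | 64% |
| Conditions, 2 + Poisson(1.5) or 2 + Poisson(3) | above median | 32–34% |
| Same | at or above median | 38–57% |

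The last two rows show that the tie rule matters for a count.

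**Power at N = 202.** The standard error of a linear interaction per SD of the modifier is 2 × 5.3 / √202 = 0.746 mg. A median split of a normal modifier multiplies the expected z by √0.637 = 0.798. Power is approximately Φ(z − 1.96); the far tail is added for the smallest interaction.

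| Interaction per SD | z, continuous | Power | z, split | Power |
|---|---|---|---|---|
| 2.1 mg | 2.82 | about 80% | 2.25 | about 61% |
| 1.5 mg | 2.01 | about 52% | 1.60 | about 36% |
| 0.5 mg | 0.67 | about 10% | 0.53 | about 8% |

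Restoring 80% power after the split would take 202 / 0.637 = 317 evaluable participants.

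**Choosing the cut after seeing the data.** In 4,000 simulated null trials per setting (N = 202, normal modifier, no true interaction), the largest interaction statistic over several candidate cuts was tested at nominal 5%:

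| Rule | Type I error |
|---|---|
| Fixed median | about 5% |
| Best of 3 cuts | 11.6% |
| Best of 5 cuts | 15.4% |
| Best of 9 cuts | 21.2% |

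**The case against.** Grouped subgroups with an interaction term and forest plots are conventional. The stated question is whether effects differ between groups, and a grouped test answers it directly. The efficiency argument also runs both ways: if the effect changes by a step at the median of a normal modifier, the linear term keeps only 2/π = 64% of the information and the split is the better test. The interactions that show a clear gain are large. Around an average effect of 2.1 mg, a slope of 2.1 mg per SD means no effect one SD below the mean and 4.2 mg one SD above it. At 0.5 mg per SD neither test is informative.

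All of this stands, and it makes the point an improvement rather than the correction of an error.

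A reader might also infer more than the SAP supports:

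- That all three cuts are open. For number of conditions the median is named; only the handling of ties is missing.
- That age is certainly cut, or that activity is certainly grouped at baseline. Both are reasonable inferences from the stratified analysis, but neither is stated.
- That cuts will be searched for. Nothing says so; the SAP merely does not prevent it for age and activity. The protocol was not available and may define these groups.

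What the objection does not answer is that a continuous term needs no cut, while the plan tests at 0.05 without multiplicity adjustment and leaves two of the cuts unstated.

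**Conclusion.** The point holds as a low-cost improvement to the subgroup analyses. Grouping is explicit for number of conditions and activity and implied for age. Cuts are unstated for age and activity, and activity also lacks a measure and a time point.

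The loss of about a third rests on a near-median cut, a roughly normal modifier and a linear interaction. It is not a fixed property of this plan, because the cuts and distributions are unknown. The fall in power from about 80% to about 61% applies to a large interaction under the same assumptions. The inflated error rates apply only if cuts are chosen by their results.

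It would be wrong to read this as a weakness in the main trial result: the primary analysis in section 4.5.1 does not depend on any of these groupings.

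**What to change.** In section 4.7:

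- Make the interaction test for age, number of chronic conditions and baseline average acceleration a continuous covariate-by-treatment term, retaining the covariate's main effect. Baseline activity volume is already in the primary model, so that factor needs only the product term.
- State that the activity modifier is the baseline accelerometer measure, if that is the intention.
- Keep groups for the forest plot only. Fix the cuts for age and activity, and the rule for counts equal to the median, from pooled baseline data without reference to outcome.

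The cost is SAP wording; no new data are needed. The introduction provides for amendment and for finalisation before database lock. If lock has passed, the continuous tests can be reported as unplanned, as the introduction also allows. The downside is that a linear term may miss a step or curved pattern. The displayed groups would still show it, though without a formal test.

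### Section 4.7 of the SAP ranks within-stratum regressions above the interaction that its aim needs, and sex falls under two inconsistent rules

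*SAP*

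**What the plan says.** Section 4.7 lists eight subgroup factors, sex among them, and states its aim as a comparison of the intervention effect between groups. Its method is then ranked: "The main analysis for each subgroup will involve using the same analytic principles as the primary analysis, but stratifying by the subgroup". These stratified models estimate the mean difference in activity within each subgroup. A subgroup-by-treatment term follows as a further analysis, and the forest plot is to carry a 95% CI for the interaction. The section gives no significance level of its own and no rule for when a difference may be claimed.

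Section 4.5.2.4 takes the opposite order for gender and ethnicity. It fits the interaction first, and then: "If the interaction term is statistically significant at the 10% level then stratified analyses will be performed for that factor". Sections 4.5.1 and 4.5.2.2 use gender and sex for the same stratification factor, so this is the same variable as sex in section 4.7. Ethnicity appears in 4.5.2.4 but not in the list in 4.7.

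Section 4.1 sets the general rule: "All tests and reported p-values will be two-sided, where a p-value of < 0.05 will be considered to be statistically significant". It names no exception for interactions and plans no adjustment for multiple testing.

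**The concern.** Whether an effect differs between two groups is a question about the difference between two estimates. Two separate regressions, each tested against zero, do not answer it. One stratum can reach p < 0.05 and the other miss it although the true effect is the same in both, because each stratum holds only part of the sample. When the stratified models are labelled the main analysis and each may carry a significance label, the plan leaves that misreading open and does nothing to bar it.

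The double treatment of sex is a separate defect and needs no assumption about subgroup sizes. With an interaction p of 0.30, section 4.5.2.4 triggers no stratified analysis while section 4.7 requires one. With p of 0.07, the interaction is significant by the level in 4.5.2.4 and not by the level in 4.1. At stake is how subgroup results are read and reported. The primary result is not affected.

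**Working it through.** **Inputs from the SAP.** Section 1.2.6 plans to "detect a minimum clinically significant difference of 2.1 mg", "assuming a standard deviation of 5.3 mg", with 80% power at the 5% level and 202 participants needed before allowance for losses. Section 1.2.2: "Participants will be randomised 1:1". Section 4.1: tests are two-sided.

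**Assumptions.** The SAP gives no subgroup sizes, so I take splits from 50:50 to 90:10 of the 202, with 1:1 allocation inside each stratum. The true effect is a uniform 2.1 mg. Power is from the unadjusted two-sample t-test.

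**Step 1: reproduce the planned size.** With n per arm, the non-centrality is 2.1 / (5.3 × √(2/n)). At n = 101 this is 2.82 on 200 degrees of freedom, giving power 0.800. The planned 202 is reproduced.

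**Step 2: power within a stratum.**
- 50:50 split, 50.5 per arm in each stratum: non-centrality 2.1 / (5.3 × √(2/50.5)) = 1.99, power 0.505.
- 25:75 split, 25.25 and 75.75 per arm: non-centralities 1.41 and 2.44, powers 0.281 and 0.678.

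**Step 3: chance that exactly one stratum is significant.** The strata contain different people, so P = p₁(1 − p₂) + p₂(1 − p₁).
- 50:50: 2 × 0.505 × 0.495 = 0.50.
- 25:75: 0.281 × 0.322 + 0.678 × 0.719 = 0.578.

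| Split | Power, larger stratum | Power, smaller stratum | Exactly one significant |
|---|---|---|---|
| 50:50 | 0.505 | 0.505 | 50% |
| 60:40 | 0.581 | 0.421 | 51% |
| 70:30 | 0.648 | 0.329 | 55% |
| 75:25 | 0.678 | 0.281 | 58% |
| 80:20 | 0.707 | 0.233 | 61% |
| 90:10 | 0.757 | 0.135 | 69% |

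Equal halves are the mildest case shown.

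**Step 4: the interaction test on the same data.** Under a uniform effect its false-positive rate is its nominal 5% per factor. A simulation of 3,000 trials of 202 participants with 50:50 factors gave 5.3%. Its precision is limited. At 50:50 the standard error is 5.3 × √(2/50.5 + 2/50.5) = 1.49 mg. The interaction detectable with 80% power is (1.96 + 0.84) × 1.49 ≈ 4.2 mg, and power for an interaction of 2.1 mg is 29%.

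**Step 5: the two rules for sex side by side.**

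| | 4.5.2.4 | 4.7 |
|---|---|---|
| First step | interaction | stratified models |
| Stratified models run | triggered at the 10% level | always |
| Level for the interaction | 10% | none given; 5% from 4.1 |

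**The case against.** Four stronger readings are tempting, and the SAP does not support them.

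- *That the SAP will declare subgroup differences by comparing stratum p-values.* It says no such thing. The stratified models are there to estimate mean differences, the interaction term is prespecified, and its 95% CI is to appear on the forest plot. The 50% and 58% therefore describe what would happen if someone made that comparison. What stands is the ranking of main and further, and the absence of a sentence tying claims to the interaction.
- *That the two rules for sex let the analyst report whichever looks better.* This goes too far. Section 4.7 already requires the sex strata and the interaction to be produced. Section 4.5.2.4 says when stratified analyses follow and does not literally forbid them otherwise. Both sections build on the primary model, so the estimates should be essentially the same. What stays open is the order of testing and the status of an interaction p between 0.05 and 0.10.
- *That a 10% level for interactions is an error.* A specific screening level can sit beside a general 5% rule, and the low power in step 4 is a reason to choose one. The fault is that sex has that level in one section and not in the other.
- *That the error rate over many interaction tests measures this flaw.* Eight independent tests at 5% give 1 − 0.95⁸ = 34% for at least one false positive, but that would remain after the ranking is corrected. Section 4.1 openly plans no adjustment. It is a reason to call the results exploratory.

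**Conclusion.** The point holds as a mismatch between aim and method in section 4.7, and as an inconsistency over sex between sections 4.5.2.4 and 4.7. The interaction is planned and will be shown; what it lacks is first place and a rule that subgroup claims depend on it. Conditional on stratum p-values being compared, a uniform 2.1 mg effect would look confined to one stratum in about 50% of trials per factor for equal halves and 58% for 25:75, against 5% for the interaction test. Those figures rest on the SAP's SD and planned 202, on assumed subgroup sizes and on an unadjusted comparison; covariate adjustment or a different number analysed would move them. The inconsistency over sex rests on the text alone. Both should be corrected, but neither touches the primary analysis.

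**What to change.** In section 4.7:
- Make the treatment-by-subgroup interaction estimate with its 95% CI the main subgroup analysis, and the sole basis for any claim that the effect differs. Fit it in one model on the primary, complete-case population. Section 3.3 uses the heading full analysis set for the imputed ITT population, which is a sensitivity analysis, so that term should be avoided here.
- Present stratum estimates with 95% CIs as descriptive.
- Label all subgroup results exploratory and state how many interactions are tested: nine if ethnicity joins the eight factors listed.

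Across sections 4.5.2.4 and 4.7, handle sex and ethnicity once, under one rule and one prespecified significance level. Either 5% or 10% can serve, provided that it is stated and that section 4.1 refers to it if it differs from the general level.

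The cost is a change of SAP wording. No new data, recruitment or model is needed.
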